Figure 1: Study Design. Subjects will be randomly assigned to the control, low- dose exercise, or high-dose exercise group. Intervention will occur on Days 1-5 depending on group assignment. Assessment of physical and pain measures occurs on Days 1, 3, 5, and 6.

Subjects will then be set-up for training on the exercise protocol, physical pain measures and pedometer use. Subjects will become familiarized with the exercise protocol, including the physiological measures to be assessed [heart rate (HR)], the Borg Rate of Perceived Exertion (RPE) Scale, and the treadmill speed at which they will be walking (3.5mph). Typical walking speed to engage in moderate intensity physical activity (3-5.99 METs) is a brisk pace of 3-4 mph and anticipated activity heart rate will be 60% of age-adjusted maximal heart rate⁸. The subject will walk on the treadmill for 5 minutes to become comfortable with the exercise procedure. Subjects will be instructed to step up onto the treadmill and stand on the sides not the belt or belt deck. The researcher will slowly raise the speed to 2 mph. The subject will be instructed to step on the treadmill at this time. After 30 seconds, the speed will be ramped up to 2.5 mph and after another 30 seconds, the speed will be ramped up to their prescribed session speed. They will also be instructed to walk with a natural gait pattern, allowing bilateral arm swing. To allow a natural arm swing, subjects are unable to hold onto the treadmill arm rails. Subjects will be introduced to the Borg RPE scale and asked to provide subjective feedback on their level of exertion at the initiation of and during the final minute of this 5-minute training period. Subjects will be given a standard pedometer and instructed to wear it on their wrist during all hours (except showering/bathing) for the 6 consecutive days during the week in which they participate in data collection. The digital screen will be covered as awareness of daily step counts may influence participant's normal daily physical activity. Subjects will be given an instruction sheet for testing sessions and pedometer use.

During the enrollment period subjects will also be given a full description of all sensory and pain measures that will be taken. With initial consent, all subjects will be allowed to experience all sensory/pain measures before full enrollment. All sensory and pain assays are

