
Procedures: Following the screening and training session, subjects will be randomized to one of four conditions (Control, Low Frequency of Exercise, Moderate Frequency of Exercise, and High Frequency of Exercise) and scheduled for their exercise and data collection sessions (Figure 1). Subjects in the control group will be scheduled for three experimental sessions within a five-day period: Days 1, 3, and 5. Control subjects will complete all of the physical and sensory/pain tests following a 30-minute period of rest (no physical activity) on each of these days. These subjects will be set up in a private room with various reading materials during this time period. Subjects in the low frequency of exercise group will be scheduled for three exercise sessions within a five-day period: Days 1, 3, and 5. Subjects in the moderate frequency exercise group will be scheduled for five exercise sessions within a five-day period: Days 1-5. Subjects in the high frequency exercise group will be scheduled for ten exercise sessions within a five-day period: Days 1-5. For all subjects, physical and sensory/pain measures will be taken on exercise days 1, 3, and 5, 5 and 30 minutes after exercise, and also on Day 6 (no exercise).

Exercise Session

Subjects will arrive at the Health Science Exercise Physiology Lab on their scheduled exercise days. Sessions will be scheduled at the same approximate time each day to control for factors that may influence exercise performance. At the initiation of each exercise session, HR measures will be taken. At the initiation of the session on days 1, 3, and 5, pain measurement will be made using the 3 assays described in detail above. For each assay, pain will be individually defined on a 0-10 visual analog scale (VAS), a common scale used in human pain testing¹³. Each assay is safe and produces only mild escapable acute (<1 min) pain. Pain measurements will be completed on both the calf and volar non-dominant forearm for each subject. On days 2 and 4 for subjects in the moderate frequency and high frequency of exercise group, sensory and pain measures are not collected.

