PARQ and You will be used to determine if a participant is not healthy enough to participate in the study due to a presence of a heart conditions, chest pain, dizziness, joint problems, and drug use.

AHA/ACSM Health Fitness Facility Preparticipation Screening Questionnaire collects past medical history, current health issues, and cardiovascular risk factors that would indicate exclusion from participation.

Physical performance

For all conditions, we will evaluate daily normal physical activity and intensity with a pedometer.

The International Physical Activity Questionnaire long version¹⁴ (IPAQ-long) will be used to obtain estimates of weekly physical activity. Based on subjects' responses, the total energy

expenditure for participation in different physical activities can be calculated. The total energy expenditure is used to categorize subjects based on the amount of vigorous, moderate, or low intensity activity they engage in.

The Borg RPE scale¹⁵ is used to collect a subjective measure of fatigue. The Borg RPE scale ranges from 6 (no exertion at all) to 20 (maximal exertion). This scale is based on expected heart rate during minimal, moderate, and vigorous intensity exercise. A subject who rates their exertion level as a 12 on this scale is working at a moderate intensity and should have a heart rate of 120 beats per minute (12×10).

All exercise sessions will be monitored using two wireless cameras (Dropcam Wireless Video Camera) to avoid influence of social observation while continuing to monitor subject's performance and physiological measures (HR) of exercise. Video will be transmitted via a secure Wi-Fi signal to a university-owned laptop computer. Either a PI or graduate student will view the real-time video to ensure subject's safety and continued optimal performance. Video will be transmitted via secure wireless signal to ensure confidentiality.

Pain measures –As described above, the three tests are for tactile sensitivity, thermal pain, and pressure pain.

Cutaneous Stimulators –

For cutaneous mechanical sensation, we will use standard von Frey filaments (Touch Test Sensory Evaluators; North Coast Medical). These filaments (ranging from 0.008g to 1.0g) are used to measure threshold for sensation to innocuous stimulation. See above for full description of assay.

Radiant Heat –

For radiant thermal heat measurements, we will use a standard “Hargreaves” apparatus (IITC Thermal Stimulus Apparatus) (see image to right).

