The collection of data has been described in detail under "Procedures". The primary outcome is a change in Quantitative Sensory Testing. This includes a series (8) of Quantitative Sensory Tests measured at baseline and at the completion of the 1-week intervention period. These tests are measured at two sites (calf and forearm). Significant differences between groups for 7 of the tests (per body site) will be identified using a one-way ANOVA comparing percent change from baseline (post-test (i.e. day 6)/baseline test (i.e. day 0)). Given the number of statistical tests that will be required for the primary outcome measurements, $p < 0.01$ will be utilized for each body site. An additional test for mechanical sensitivity will be measured at each site using a rank sum test at $p < 0.05$.

The secondary outcomes for this study include (1) HR during exercise, (2) Borg RPE before and after exercise and (3) testing "acute" effects of exercise on QST testing. HR during exercise and Borg RPE are measured to make sure that exercise causes a change in HR and/or perceived exertion. HR and Borg RPE data will be analyzed using percent change from start of exercise (post-exercise/pre-exercise) with two-way ANOVA for 3 treatment groups (3-day, 5-day, 10 day) across time (day 1, 3, 5) with an adjusted p value of $p < 0.03$. Control group will not be included in that analysis as HR was not measured on the control days and perceived exertion is at "0" on all days. For acute effects of exercise, participants were given 8 QST tests (on each forearm and calf) 5 min and 30 min after each exercise (or control session) on days 1, 3, and 5. Significant differences between groups for these tests (per body site) will be identified using a two-way MANOVA comparing percent change from baseline (post-exercise/baseline test (i.e. day 0)) across the three days (day 1, day 3, day 5) and at the 5 min and 30 min time QST measuring point. Given the number of statistical tests ($n=8$) that will be required for the QST secondary outcome measurements, $p < 0.01$ will be utilized for each body site.

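### The only analysis named for HR and Borg RPE compares exercise arms and days with each other, so it cannot show the change common to all sessions that these measures are meant to confirm

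*Combined protocol and SAP*

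**What the plan says.** Section 8 lists HR and Borg RPE as secondary outcomes and states their purpose: "HR during exercise and Borg RPE are measured to make sure that exercise causes a change in HR and/or perceived exertion". The variable is "percent change from start of exercise (post-exercise/pre-exercise"), and the analysis is a "two-way ANOVA for 3 treatment groups (3-day, 5-day, 10 day) across time (day 1, 3, 5") at an adjusted level of 0.03. It adds: "Control group will not be included in that analysis". It names no paired pre/post test, no test of the ratio against no change, and no confidence interval for the mean change. The only other HR test in Section 8 compares baseline HR between the four groups, which does not bear on change with exercise.

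Section 3 describes one exercise session for everyone: "the treadmill speed at which they will be walking (3.5mph"), for 30 minutes, with a single anticipated heart rate of 60% of the age-adjusted maximum. The exercise arms differ in the number of sessions in the week (3, 5 or 10).

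**The concern.** The stated purpose asks whether HR and RPE move during a session. The named test asks whether the post/pre ratio differs between arms, between days, or in its pattern across both. If every session works as intended and to a similar degree, the answer to the second question is no. The ANOVA would then usually be non-significant, exactly as it would be if the walk had no effect on HR or RPE. A reader could take that for a failed manipulation check, and the plan offers no other inferential result to set against it.

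**Working it through.** The plan gives no sample size, power or SD for HR or RPE, so there is no figure of its own to reproduce.

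**Inputs from the documents.** Three exercise arms; days 1, 3 and 5; 10 (minimum) to 15 (goal) people per arm (Section 5); level 0.03.

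**Step 1, algebra.** Write the ratio for person *i* in arm *g* on day *t* as y = 1 + c + e, where c is the change common to all sessions. The arm effect uses (arm mean − grand mean), the day effect (day mean − grand mean), and the interaction (cell mean − arm mean − day mean + grand mean). The constant 1 + c drops out of each. It also drops out of both error terms, which are deviations from person and cell means. All three F statistics are therefore free of c, for any SD, correlation or sample size.

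**Step 2, numerical check.** In one simulated data set (10 per arm, day as a within-person factor), F was 0.863 for arm, 3.742 for day and 1.547 for interaction. Adding 30 or 60 percentage points to every session left all three unchanged.

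**Step 3, rejection rates.** 4,000 simulated trials per setting, level 0.03. Assumed, because the documents give no values: between-person SD 10 and within-person SD 8 percentage points, no arm or day differences.

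| Per arm | Common change | Arm F | Day F | Interaction F | Any of the three | Overall mean vs no change |
|---|---|---|---|---|---|---|
| 10 | 0 | 0.030 | 0.028 | 0.031 | 0.086 | 0.034 |
| 10 | +5% | 0.034 | 0.030 | 0.026 | 0.088 | 0.584 |
| 10 | +10% | 0.029 | 0.028 | 0.027 | 0.081 | 0.993 |
| 10 | +60% | 0.035 | 0.032 | 0.027 | 0.091 | 1.000 |
| 15 | 0 | 0.031 | 0.034 | 0.029 | 0.090 | 0.028 |
| 15 | +5% | 0.031 | 0.028 | 0.031 | 0.087 | 0.789 |
| 15 | +60% | 0.028 | 0.036 | 0.032 | 0.094 | 1.000 |

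The F-test columns stay at the error rate. If the three tests were independent, the chance of any rejection would be 1 − 0.97³ = 0.087, in line with the table.

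**Step 4, the last column by formula.** SE of the overall mean = √[(10² + 8²/3)/(3n)]. For n = 10 this is √(121.33/30) = 2.01 points, on 3(n − 1) = 27 df with critical t = 2.29. A 5-point change has noncentrality 5/2.01 = 2.49 and power 0.58. The 97% interval has half-width 2.29 × 2.01 = 4.6 points. For n = 15 the SE is 1.64, critical t 2.25, power 0.78 and half-width 3.7 points.

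**Step 5, sensitivity.** With an assumed ratio SD of 0.10 to 0.50 and within-person correlation of 0 to 0.7, the 97% half-width for the overall mean ratio, t × SD × √[(1 + 2ρ)/3]/√(3n), runs from 0.02 (SD 0.10, ρ = 0, n = 15) to 0.19 (SD 0.50, ρ = 0.7, n = 10). Over the same range each F test rejected 0.026 to 0.033 of the time at every common ratio tried from 1.0 to 2.0.

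**Step 6, the intercept.** Software prints an intercept test with the ANOVA, but on the post/pre ratio its default null is 0, whereas no change is 1. In Step 3 that test rejected in every simulated trial, including those with no change.

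**The case against.** The best reply has four parts. First, Section 8 gives a reason for measuring HR and RPE and does not say that the ANOVA tests that reason; an arm-by-day comparison is a sensible check of equal intensity. Second, reported cell means would show the rise. Third, Section 3 says HR is watched live so that the person is working at moderate intensity, which is a check in every session. Fourth, few would doubt that brisk walking raises heart rate.

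All four bear on weight. None supplies the missing inference: the plan makes this a secondary outcome with a significance level, and then applies that level only to differences between arms and days. Live monitoring guides the session but yields no planned estimate.

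Several stronger readings are tempting and are not supported:

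- *That the documents predict a ratio of 2.0 for RPE and 1.2 to 2.0 for HR.* These come from combining the scale minimum of 6, the entry range of HR 60 to 100, and Section 4's remark that a person rating 12 "is working at a moderate intensity and should have a heart rate of 120 beats per minute". That remark explains the scale; it is not a forecast for this walk. The argument needs no such ratio.
- *That the whole ANOVA would be non-significant 97% of the time.* That holds for each F test; for all three together it is about 91% to 92%.
- *That a significant F would establish that exercise changed HR or RPE.* It may be a false positive, and even if real it gives neither the direction nor the arm.
- *That the data are already collected.* Section 8 mixes past and future tenses, so this is not established.

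**Conclusion.** The point holds and should be corrected. As written, the analysis of HR and RPE cannot answer the question the plan sets for it: a change shared by all sessions is invisible to all three F tests, which reject at about 3% each and 8% to 9% jointly whatever its size. The cancellation is algebraic and rests on no assumed SD. That the expected change is a shared one is an inference, but a firm one, from the identical session description and the single anticipated heart rate. The SDs and correlations affect only the illustrated precision of the replacement.

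The ANOVA would still detect a response that differs by arm or day. The consequence is confined to a secondary manipulation check: a reader should not infer that the primary day-6 sensory testing analysis is compromised or that exercise intensity goes unmonitored.

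**What to change.** In Section 8, for HR and RPE separately:

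- Make the manipulation check the mean within-session post/pre ratio, overall (the test) and by arm (intervals), with a 97% confidence interval to match the plan's 0.03.
- Compare it with 1, the no-change value on the ratio as defined (0 only if re-expressed as percent change or log ratio). Do not use a default intercept test against 0 on the ratio.
- Estimate it from a repeated-measures or mixed model with participant as the repeated unit.
- State which HR reading is the post-exercise value. Section 8 refers both to HR during exercise and to a post-exercise value, and Section 3 names an end-of-walk reading for RPE but not for HR.
- State which session's value enters (one named session, or the participant's mean for the day) when a day has several: "Subjects in the high frequency exercise group will be scheduled for ten exercise sessions within a five-day period".
- Score RPE on its own scale so that the ratio is defined. Section 4 says "The Borg RPE scale ranges from 6 (no exertion at all) to 20 (maximal exertion"), while Section 8 puts control exertion at 0; a pre-exercise 0 would make the ratio undefined.
- Say whether a change in one measure suffices, since the purpose is worded as and/or.
- Keep the arm-by-day ANOVA as a check of equal intensity.

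If the data are already in hand, date the addition and label it post hoc. The cost is a short paragraph in Section 8 and no new visits. Pre- and post-exercise RPE and HR monitoring are already planned; only the HR reading to be used needs defining.

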based on well-established assays used in both healthy human participants and patients with chronic pain⁹. All assays involve either innocuous (non-painful stimuli) or acute noxious stimuli (painful stimuli) that do not damage tissue. Time between different tests will be >5 min to allow the subject to rest. Timing of testing on experimental days will be 5 minutes and 30 minutes following the completion of exercise or 30 minutes of rest (for control subjects and for all subjects on day 6). For all testing days order will proceed in the following manner. Training and description of each measure is as follows:

Cutaneous mechanical sensitivity assay¹⁰: Enrolled participants will be asked to sit in a chair (chair provided with arm-rests). Assay involves determining the sensitivity threshold for innocuous cutaneous stimulation. Stimulation is provided with standard sensory evaluator filaments (see equipment section below for image of filament). These are small nylon filaments each apply a single force (ranging from 0.008gram to 1.0gram). Before the start of the first experimental trial, subjects will be allowed to feel and manipulate the filaments. Starting with the smallest filament (0.008g; below the sensory threshold for human detection), 5 trials will be directed at the subject's forearm. During testing, subject is asked to look away from their forearm/calf. Experimenter will ask "Can you feel this" while the experimenter applies the filament to the subject's forearm or calf. With each filament, the experimenter will apply the filament 3 times in the "positive" trials. For the other 2 trials, the experimenter will not apply the filament but ask the subject, "Can you feel this?" These 2 "negative" trials will be randomly inserted with the 3 "positive" trials and are designed to test for false responses. If a subject detects ≥ 2 of the positive trials and 0 negative trials for a filament, that force will be the subject's "mechanical sensory threshold." For a single filament, if the subject detects < 2 of the real trials and/or > 0 of the false trials, the experiment will start another round of 5 trials with the next biggest filament until the sensory threshold is reached. Typical testing time for each body part (forearm and calf) is about 5 minutes.

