The heart rate monitor will be strapped to the subjects' chest to monitor HR throughout the exercise session. The purpose of monitoring HR is two-fold: 1.) to ensure the subject is working at a moderate level of intensity, and 2.) to ensure the subject is safely participating in physical activity with no abnormal or adverse changes in HR. Subjects will provide a rating of their perceived exertion on the Borg RPE scale before beginning the exercise task. Subjects will then be set-up to begin walking on the treadmill. Subjects will be reminded of the instructions for how to step onto the treadmill and the process for ramping up the speed as described in the training session. Once walking on the treadmill at the prescribed speed, subjects will be instructed to walk until the researcher returns (30 minutes). Subjects will be told that they can stop walking if they become excessively fatigued (≥ 17 on the Borg RPE scale) or experience symptoms of overexertion, such as lightheadedness and excessive sweating. The Borg RPE scale will be positioned in front of them for a visual reminder of the fatigue scale and the treadmill safety key will be secured to the subject's shorts. After 30 minutes, the researcher will return to the room. At this time, perceived exertion on the Borg RPE scale will be assessed again. The researcher will then slow the treadmill speed down to approximately 2 mph for a 2-minute cool-down. Pain measures will be completed as described above following completion of the treadmill walking at 5 minutes and 30 minutes.

Subjects will perform their exercise session alone, with no close supervision by study staff. To ensure safety during exercise, the subject will be monitored with 2 wireless video cameras. Camera 1 will be focused on the subject to visually observe the subject's performance and ensure there are no visual signs that the subject is over-exerted. Camera 2 will be focused on the treadmill interface to monitor real-time HR and ensure the subject does not adjust the speed. Video recordings from the cameras will not be saved and is only used to monitor the subject's physical response to exercise. Subjects will be unaware that they are being monitored via camera. All subjects will return on Day 6 to complete a final round of pain/sensory testing.

4. Instruments

Screening Questionnaires

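### The acute QST outcome is measured against day 0, so on days 3 and 5 it is total change from baseline; without a further assumption only day 1 can be read as a single-session effect

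*Combined protocol and SAP*

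**What the plan says.** Section 8 (Collection of data and method of data analysis) defines the acute QST outcome through a "two-way MANOVA comparing percent change from baseline (post-exercise/baseline test (i.e. day 0)) across the three days", the days being 1, 3 and 5. The numerator is fixed by the statement that "participants were given 8 QST tests (on each forearm and calf) 5 min and 30 min after each exercise (or control session"). The denominator is the day 0 test on all three days. The same section analyses heart rate and Borg RPE differently, as a post/pre ratio within the session.

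On whether there is a same-day reference, the document is not consistent:

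- Section 3, Exercise Session: "At the initiation of the session on days 1, 3, and 5, pain measurement will be made using the 3 assays". No analysis in section 8 uses this measurement.
- Section 3, paragraph on timing of testing: "Timing of testing on experimental days will be 5 minutes and 30 minutes following the completion of exercise or 30 minutes of rest".
- Section 3, Procedures, all arms: "For all subjects, physical and sensory/pain measures will be taken on exercise days 1, 3, and 5, 5 and 30 minutes after exercise". A final round follows on day 6.
- Section 3, Procedures, controls: "Control subjects will complete all of the physical and sensory/pain tests following a 30-minute period of rest".
- Section 3, Exercise Session, after the treadmill walk: "Pain measures will be completed as described above following completion of the treadmill walking at 5 minutes and 30 minutes".

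On exposure, Procedures schedules the low group on days 1, 3 and 5 and the moderate group on each of days 1 to 5. For the high group, "Subjects in the high frequency exercise group will be scheduled for ten exercise sessions within a five-day period: Days 1-5"; the split by day is not stated, nor is which session on a test day is followed by testing.

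**The concern.** An acute effect is the change produced by one session. Dividing by day 0 isolates it only if the participant starts that day's session at the day 0 level. On day 1 that is reasonable. On days 3 and 5 it requires that earlier sessions left nothing behind, and the plan does not state this. It could hardly take it for granted, since the primary outcome (day 6 against day 0, with no exercise on day 6) looks for exactly such a lasting effect.

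If there is carry-over, group differences on days 3 and 5, or pooled over the three days, could be reported as the effect of a single session when there is none. Because earlier exposure rises with assigned dose, the distortion would run along the dose comparison the trial was set up to make.

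**Working it through.** **Decomposition.** For any participant and test day,

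log(post/day 0) = log(post/same-day pre) + log(same-day pre/day 0).

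The first term is the session's effect. The second holds carry-over plus drift. Subtracting control removes drift common to all arms, such as repeat testing. It leaves acute effect plus carry-over in each exercise arm: two unknowns and one contrast per day. Testing at both 5 and 30 minutes does not help, because both readings share the second term. Separation needs an extra assumption, such as a constant acute effect over days or carry-over equal to that seen on day 6.

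**Earlier sessions, counted to the start of the test day** (Procedures; the high group assumes two sessions a day):

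| | Control | Low | Moderate | High |
|---|---|---|---|---|
| Day 1 | 0 | 0 | 0 | 0 |
| Day 3 | 0 | 1 | 2 | about 4 |
| Day 5 | 0 | 2 | 4 | about 8 |

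Day 1 is clean in the high group only if testing follows the first session of that day.

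**Size, as an illustration.** The plan has no figure to reproduce. From the documents: four groups, 15 per group (goal) or 10 (minimum), alpha 0.01. Assumed: log scale, SD 1 per reading, correlation r = 0.6 to 0.7 between any two days, no acute effect, one time point. The test is a one-way F on the group effect, which simplifies the planned MANOVA.

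- Variance of a single day minus day 0: 2 − 2r = 0.8 to 0.6.
- Variance of the three-day mean minus day 0: (1 + 2r)/3 + 1 − 2r = 0.533 to 0.400.
- Noncentrality: n × Σ(group mean − overall mean)² / variance, with 3 and 4n − 4 degrees of freedom.

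Worked case: carry-over of 0, 0.4 and 0.8 SD on days 1, 3 and 5 in every exercise arm. Three-day means are 0 for control and 0.4 for the others; the sum of squares is 0.09 + 3 × 0.01 = 0.12. With n = 15 the noncentrality is 1.8/0.533 = 3.375 to 1.8/0.400 = 4.5, giving rejection in 11.4% to 16.8% of trials.

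Proportional case: carry-over in proportion to 2, 4 and 8 sessions, the high arm reaching 0.8 SD. Three-day means are 0, 0.1, 0.2 and 0.4; the sum of squares is 0.0875; the noncentrality is 2.46 to 3.28.

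| Carry-over by day 5, no acute effect | Three-day mean, n = 15 | Three-day mean, n = 10 | Day 5 alone, n = 15 |
|---|---|---|---|
| 0.2 SD, all exercise arms | 1.4% to 1.5% | 1.2% to 1.3% | 2.0% to 2.4% |
| 0.4 SD, all exercise arms | 2.7% to 3.4% | 2.0% to 2.4% | 6.9% to 9.8% |
| 0.8 SD, all exercise arms | 11.4% to 16.8% | 6.4% to 9.1% | 42.5% to 59.1% |
| Proportional, high arm 0.8 SD | 7.6% to 11.0% | 4.6% to 6.2% | not computed |

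Day 1 alone, or a same-day pre-session reference, gives 1% throughout. The day 5 column is for scale only; section 8 does not specify a stand-alone day 5 test.

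**Cost of the alternatives.** Take a constant acute effect of 0.6 SD in every exercise arm, n = 15. The sum of squares is 0.27, so n times it is 4.05.

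- Day 1 alone: noncentrality 4.05/0.8 = 5.06 to 4.05/0.6 = 6.75; power 20% to 29%.
- Three-day mean against day 0: 4.05/0.533 = 7.59 to 4.05/0.400 = 10.1; power 34% to 49%.
- Single-day same-day change: power 14.5% if the same-day correlation is 0.5 (variance 1); the same as day 1 alone if it is 0.6 to 0.7.

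**The case against.** The strongest reply is that this is a label on a secondary outcome. Post/day 0 against control is a legitimate summary, and the pressure assay description in section 3 shows that change from baseline on each test day was intended. The type I error for the hypothesis actually tested, that groups differ in change from day 0, is not inflated. Section 8 sets the word acute off in quotation marks and describes these tests by their timing, so it can be read as meaning soon after exercise. This all stands. It makes the fault one of interpretation and does not invalidate the test.

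Second, the plan has partial safeguards. Day is part of the comparison: under the 0.8 SD equal-arm pattern, a group comparison of day 5 minus day 1 (variance 2 − 2r) would be significant in 43% to 59% of trials, more often than the three-day average. Day 6 estimates what remains without exercise. These make an unnoticed misreading less likely. They do not resolve it, because growth over days could equally be a changing acute effect, and carry-over on day 6 need not equal that on day 3 or day 5.

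Third, the larger rates need a session to do nothing at 5 and 30 minutes while earlier sessions leave 0.8 SD behind. No passage supports that combination. This limits the magnitude but not the definitional point.

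**Conclusion.** The point holds as one of definition. On days 3 and 5 the planned outcome is total change from baseline, and calling it acute needs an assumption the plan does not state. Day 1 supports an acute reading, in the high group only if testing follows the first session. The definitional conclusion needs no assumed numbers; the session counts come from the schedule, apart from the two-a-day split in the high group.

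The practical size is unknown. On the stated assumptions it runs from near nominal (about 1.4% to 3.4% at n = 15 for carry-over of 0.2 to 0.4 SD) to 11% to 17% at 0.8 SD in all exercise arms. At n = 10 the two 0.8 SD patterns give 5% to 9%.

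A reader might infer that a significant result on days 3 or 5 would be a false positive. It would not: the groups would truly differ from day 0, and only the attribution to one session would be unsupported. Nor do the documents show that carry-over exists, or that pre-session scores were collected and then ignored; the passages conflict on whether they are taken, and none settles whether controls have them. The primary day 6 analysis is unaffected. The change is worth making because it alters what the trial can claim and requires no new data.

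**What to change.** 1. Reconcile section 3 (timing paragraph, Procedures, Exercise Session) and section 8 on whether start-of-session QST is collected on days 1, 3 and 5, and in which arms, controls included.
2. If it is collected in all arms, define the acute outcome as change from the same-day pre-session score, compared between groups. Use a log ratio for heat latency and pressure threshold, a difference for VAS scores (which can be 0), and a rank-based comparison for the stepped filament threshold, as in the primary analysis. For pressure VAS use the fixed day 0 pressure, or the day's own threshold only if the same pressure is applied before and after the session. Keep post/day 0 as a total-change summary.
3. If it is not collected in all arms, limit the acute claim to day 1 and report days 3 and 5 as total change from baseline.
4. State which of the high group's sessions on a test day is followed by testing. If it is not the first, do not describe that arm's day 1 result as a single-session effect.

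The cost is wording in section 8 and reconciliation of the testing schedule; no added testing is asked for. Restricting the claim to day 1 gives up the precision of pooling, as the power figures above show. Same-day change loses precision if same-day readings correlate less closely with each other than with day 0.
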